1.3 Objectives and Purpose

The goal of this study is to determine if the addition of IPACK block to the standard of care adductor canal block is superior to an isolated adductor canal block in decreasing postoperative pain, decreasing opioid consumption, and leads to increased duration of analgesia in patients undergoing ACLR. The primary objective will be to compare opioid utilization between the two arms within the first 72 hours after surgery, including intraoperatively, as measured by morphine equivalents. Our secondary objectives are measuring patient reported pain scores in PACU at 24 hours, 48 hours, and 72 hours, and at the first postoperative visit (POD 7).

2 Study Design and Endpoints

Arm 1: Experimental	Arm 2: Control
Sample Size: 50	Sample Size: 50
Medication: 15 mL of 0.25% Bupivacaine block of the saphenous nerve injected under ultrasound guidance via adductor canal and IPACK block with 20 mL of 0.25% Bupivacaine injected into the Interspace between the Popliteal Artery and Capsule of the Knee	Medication: 15 mL of 0.25% Bupivacaine block of the saphenous nerve injected under ultrasound guidance via adductor canal

2.1 Description of Study Design

RECRUITMENT PHASE/CONSENTING PHASE:

Surgeons will identify eligible patients via Epic during their initial clinic visit and discuss the study. Surgeons will provide research coordinator with the name and medical record number of eligible patients. If the patient meets the inclusion criteria outlined below and is agreeable, subjects will be first introduced to the study during one of their presurgical clinic visits and then consented on the day of surgery by a member of the research team. Patients will be made acquainted with the study prior to surgery. On DOS when they arrive 1.5/2 hours before surgery, we (study team members) will consent them in a private room and provide ample time to discuss and review any questions or concerns they may have.

BASELINE ASSESSMENTS:

Subjects will complete a baseline VAS McGill Pain scale, Kujala, KOOS-PS and Tegner Activity Scale

RANDOMIZATION PHASE:

Subjects scheduled to undergo ACLR with BPTB autograft will be randomized to either ACB with IPACK block or to ACB only. A randomization scheme will be created prior to start of study enrollment using the randomizer.org website to generate the assignment. Block randomization is commonly used in clinical trial design to reduce bias and achieve balance in the allocation of participants to treatment arms throughout the course of the study. Randomized block design allows us to account for variables so that observed differences are largely due to true differences between treatments and not to the variable. We will create blocks of four patients and in each block, two patients will be assigned to the IPACK + ACB group, and two to the ACB only

CONFIDENTIAL

This material is the property of the NYU School of Medicine and Langone Medical Center. Do not disclose or use except as authorized in writing by the study sponsor

group. Thus, patients in both groups will be evenly spread from the beginning to the end of the study.

A research coordinator will place the randomization results in sealed envelopes prior to recruitment. Each subject enrolled in the study will be assigned a number and the sealed envelope assigning the subject to the IPACK + ACB or ACB only will be opened on the day of surgery after the patient has signed consent agreeing to participate in the study.

Patients will be blinded to their group allocation. During peripheral block patients are sedated and postoperatively, the areas of infiltration will be covered by bandage.

TREATMENT PHASE:

Patients in both the study and control group will receive the standard of care adductor canal block. This consists of 15mL of bupivacaine (0.25%) Injected under ultrasound guidance in the saphenous nerve via the adductor canal. Patients in the study group will receive the additional IPACK block performed using 20 mL of bupivacaine (0.25%) injected into the interspace between the popliteal artery and capsule of the knee.

[figure not shown]
POST-OPERATIVE PHASE:

After initial recruitment, subjects' pain will be assessed via visual analog scale (VAS) by nursing staff during the post-operative period as per standard of care in the post anesthesia care unit, and by the research staff prior to leaving the surgical center. The VAS pain scores are collected and documented in the patient's electronic medical record. Additionally, a standardized regimen of pain medication will be given to all subjects who are enrolled. The pain medications given to patients are standard of care medication 325-5 mg Percocet and vary based on pain level. This is determined by the clinical staff caring for each patient. While the patient is in the PACU prior to discharge, an authorized research member will visit the patient and obtain a pain score using the VAS and McGill Pain Scale. Data on PACU opioid use documented in the electronic medical record will be collected. On POD1, POD 2 and POD 3, a phone call or email survey will be sent to the patient to collect additional data on opioid use at home as well as a VAS score at 24, 48, and 72 hours after surgery.

CONFIDENTIAL

This material is the property of the NYU School of Medicine and Langone Medical Center. Do not disclose or use except as authorized in writing by the study sponsor

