12.1	FUNDING SOURCE.....	25
12.2	COSTS TO THE PARTICIPANT	25
12.3	PARTICIPANT REIMBURSEMENTS OR PAYMENTS	25
13	CONFLICT OF INTEREST POLICY.....	25
14	REFERENCES	26
15	ATTACHMENTS	27
15.1	OPIOID EQUIVALENTS.....	27
15.2	BASELINE ASSESSMENTS.....	ERROR! BOOKMARK NOT DEFINED.
15.3	MEDICATION USAGE RECORD	ERROR! BOOKMARK NOT DEFINED.

CONFIDENTIAL

This material is the property of the NYU School of Medicine and Langone Medical Center. Do not disclose or use except as authorized in writing by the study sponsor

List of Abbreviations

ACLR	Anterior Cruciate Ligament Reconstruction
BPTB	Bone Patellar Tendon Bone
IPACK	Interspace between the Popliteal Artery and Capsule of the Knee
ACB	Adductor Canal Block
ASA	American Society of Anesthesiologist Score
BMI	Body Mass Index
DOS	Day of surgery
VAS	Visual analog scale
AE	Adverse event
SAE	Serious adverse event
IV	Intravenous
ITT	Intention-to-treat
PACU	Post-Anesthesia Care Unit
PO	Taken orally
CI	Confidence interval
SD	Standard deviation; a parameter that characterizes a population distribution
SE	Standard error
ANOVA	Analysis of variance; a linear model
NSAID	Non-steroidal anti-inflammatory drug

CONFIDENTIAL

This material is the property of the NYU School of Medicine and Langone Medical Center. Do not disclose or use except as authorized in writing by the study sponsor

Protocol Summary

Title	Adductor Canal Block and IPACK Block vs. Isolated Adductor Canal Block for Post-Operative Analgesia Following ACL Reconstruction with Bone Patellar Tendon Bone Autograft: A Single Center Randomized Placebo-Controlled Trial.
Brief Summary	A randomized, single-blind, single-center study measuring the effects of adductor canal block combined with IPACK infiltration compared to adductor canal block alone on post-operative pain and opioid consumption in patients undergoing ACL reconstruction with Bone Patellar Tendon Bone Autograft
Objectives	To determine if the addition of an IPACK block to the standard adductor canal block is superior to an isolated adductor canal block in controlling post-operative pain and decreasing postoperative opioid consumption in patients undergoing ACLR with Bone Patellar Tendon Bone Autograft
Methodology	Randomized, single-blind, single-center study

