2.2 Schematic of Study Design

CONFIDENTIAL

This material is the property of the NYU School of Medicine and Langone Medical Center. Do not disclose or use except as authorized in writing by the study sponsor

3 Study Enrollment and Withdrawal

The researchers will approach patients scheduled for primary ACLR and are eligible for participation in the study. Anesthesiology/Sports Medicine attendings, fellows, residents, and authorized researchers will consent and enroll patients pre-operatively.

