3.6 Total Number of Participants and Sites

Recruitment will end when 100 participants have been enrolled. It is expected that there will be subjects enrolled who will be lost to follow up and be evaluated by intention-to-treat. The sites for enrollment will be the NYU Langone Orthopedic Hospital and NYU Ambulatory Surgery Center at 38th street.

CONFIDENTIAL

This material is the property of the NYU School of Medicine and Langone Medical Center. Do not disclose or use except as authorized in writing by the study sponsor

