6.4 Enrollment/Randomization/Masking Procedures

We will utilize randomization.com to generate a block randomization assignments for all 100 participants. Someone that is not a stakeholder in the study will make randomization envelopes, which include the study ID number, the treatment assignment, and dosage specifics. These randomization envelopes will then be distributed to the anesthesiologist pre-operatively by the authorized researcher after informed consent is obtained.

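### A fixed, published block size of four lets a fully informed enroller predict up to a third of allocations, and sections 2.1 and 6.4 disagree on who prepares the envelopes

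*Combined protocol and SAP*

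**What the plan says.** **Blocks.** Section 2.1 (Randomization Phase) states: "We will create blocks of four patients and in each block, two patients will be assigned to the IPACK + ACB group", the other two going to ACB alone. No section varies the size. Section 6.4 describes one list and mentions no stratification: "We will utilize randomization.com to generate a block randomization assignments for all 100 participants". Section 3.6 sets the total ("Recruitment will end when 100 participants have been enrolled") and names two facilities.

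**Masking and enrolment.** The Protocol Summary calls the trial a "randomized, single-blind, single-center study", and section 2.1 names only patients as blinded. Under section 6.4 a researcher passes the envelope to the anesthesiologist after consent. Section 3 opens with: "Anesthesiology/Sports Medicine attendings, fellows, residents, and authorized researchers will consent and enroll patients pre-operatively". Section 3.4 allows the treating surgeon or anesthesiologist to take written consent on the day of surgery.

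**Envelopes.** Section 2.1: "A research coordinator will place the randomization results in sealed envelopes prior to recruitment". The same section has surgeons send a research coordinator the names of eligible patients. Section 6.4: "Someone that is not a stakeholder in the study will make randomization envelopes". Section 2.1 names randomizer.org as the generator; section 6.4 names randomization.com. Both sections link envelopes to a study number and hold them back until after consent. Neither says that they are opaque or must be used in sequence.

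**The concern.** With one known block size, past allocations reveal future ones. Once two patients in a block have gone to the same arm, the rest of the block is settled, and the fourth place is always settled. Sealing the envelope and opening it after consent protects its contents, but this inference never uses the envelope. It needs only the allocations already made, and clinicians who perform or attend the blocks see some of these.

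There is room to act on a prediction, without any intent to do so. Section 4.2.2 verifies eligibility and takes consent on the day of surgery, before randomization. Section 3.2 includes an exclusion that rests on the investigators' judgement of whether a patient can comply. Section 5.1 says the choice of block depends on physician preference, so some clinicians may favour an arm (section 4.1.2 says instead that IPACK is not standard at the institution; the two statements conflict). If borderline patients were handled differently according to the expected arm, the arms would differ before treatment began.

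The envelope conflict is a separate weakness. Under section 2.1, a role within the recruitment pathway could know the whole list, whatever the block size.

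**Working it through.** **Inputs.** Block size 4, split 2:2 (section 2.1); 100 participants (section 3.6); 50 per arm (section 2); one list (section 6.4).

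**Plan's own figure.** 100 / 4 = 25 complete blocks; 25 × 2 = 50 per arm. This agrees with the plan, which gives no predictability figure.

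**Share that is certain, all earlier allocations in the block known.** A 2:2 block has 6 equally likely orders.
- AABB and BBAA: places 3 and 4 are certain (2 each).
- ABAB, ABBA, BAAB and BABA: only place 4 is certain (1 each).
- Certain places: 2 × 2 + 4 × 1 = 8 of 6 × 4 = 24, or 33.3%.
- Over 25 blocks the number certain is 25 + Binomial(25, 1/3): mean 33.3, 95% range 29 to 38, minimum 25, maximum 50.

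**Best-guess accuracy, same observer.** Place 1: 1/2. Place 2: 2/3. Place 3: (1/3) × 1 + (2/3) × 1/2 = 2/3. Place 4: 1. The mean is (1/2 + 2/3 + 2/3 + 1) / 4 = 17/24 = 70.8%, against 50% with no information.

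**Partial knowledge.** Assume that the place in the block is known and that each earlier allocation is known independently with probability q. Place 3 is certain with probability q²/3, and place 4 with probability q² (both patients in the arm already filled must have been seen). The share is (q²/3 + q²) / 4 = q²/3.

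| q (assumed) | Share certain |
|---|---|
| 1 | 33.3% |
| 0.9 | 27.0% |
| 0.75 | 18.8% |
| 0.5 | 8.3% |

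**Alternatives, all earlier allocations known.** The mixed row comes from 3,000 simulated trials of 100, each block being 4 or 6 with equal chance, and an observer who knows the two sizes but not their order.

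| Scheme | Share certain | Best-guess accuracy |
|---|---|---|
| Fixed 4 | 33.3% | 70.8% |
| Fixed 6 | 25.0% | 68.3% |
| Mixed 4 and 6 | about 5.5% | about 69% |

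**End-of-trial balance with 4 and 6.** Both sizes are even, so a list cut at 100 stops at an even place in a block. A block of 4 cut at place 2 can stand at most 2:0; a block of 6 cut at place 2 or 4 can stand at most 2:0 or 3:1. The largest difference is therefore 2. Ten blocks of 4 and ten of 6 total 40 + 60 = 100, with no cut and a difference of zero.

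**The case against.** A reader might infer that a third of allocations in this trial will be known in advance. The documents do not support that. The figure needs an observer who knows the place in the block and every earlier allocation in it. Two facilities share what appears to be one list, many attendings, fellows, residents and researchers may enrol, and an anesthesiologist is given the envelope only for the patient at hand. This stands: one third is a ceiling, and the realistic figure depends on how much is shared. A researcher who distributes the envelopes could come close to the ceiling.

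A reader might also infer that clinicians can steer who is first approached. Patients are identified and told about the study at a presurgical visit 1 to 30 days before surgery (sections 2.1, 3.4 and 4.2.1), often before the earlier allocations in their block exist. This too stands. The main opening is the narrower one of eligibility and consent on the day of surgery.

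On the envelopes, section 2.1 does not say that the coordinator consents patients, or that the same individual receives the names and fills the envelopes. Section 6.4, the dedicated randomization section, already names a non-stakeholder. What remains is a contradiction to resolve, not evidence that a recruiter holds the list.

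Finally, it would be too strong to say that any resulting bias is beyond repair. Baseline characteristics are recorded and compared (sections 6.1 and 6.2.1), so selection on measured factors could be seen and adjusted for, although the planned tests are unadjusted. Selection on unmeasured factors could not.

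**Conclusion.** The point holds as a limited weakness in concealment. A single published block size of four, in a trial where only patients are blinded and those who learn allocations belong to a group that may also enrol, makes up to 33% of assignments certain in expectation. The ceiling assumes full knowledge of earlier allocations in the block; 27.0%, 18.8% and 8.3% follow from assumed knowledge of 0.9, 0.75 and 0.5. The documents do not show what any one person will know, and nothing in them suggests that allocation has been or will be steered. The conflict between sections 2.1 and 6.4 over the envelope preparer and the website needs no such assumption and should be corrected in any case.

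**What to change.** 1. Generate the list with randomly varying permuted blocks, for example 4 and 6. Remove the sizes from the protocol, so that only the person generating the list knows them.
2. Reconcile section 2.1 to section 6.4: the non-stakeholder generates the list (section 6.4 does not currently say who does) and prepares the envelopes, and one generator is named.
3. State that envelopes are opaque, sequentially numbered and used in order.

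Mixed sizes remove most of the certainty, from 33% to about 5.5% even for someone who knows both sizes. They do little against guessing, since best-guess accuracy stays near 69%. This is why the independent preparer and the undisclosed sizes matter as well.

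The cost is a regenerated list and a few edits. Section 3.5 keeps recruitment open until each arm has 50. A list of ten blocks of 4 and ten of 6 in random order meets that exactly; with freely drawn sizes the arms differ by at most 2 at 100 patients. The 5.5% and 69% were simulated for freely drawn sizes, so they should be recomputed if the ten-and-ten list is used.

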2.2 Schematic of Study Design

CONFIDENTIAL

This material is the property of the NYU School of Medicine and Langone Medical Center. Do not disclose or use except as authorized in writing by the study sponsor

3 Study Enrollment and Withdrawal

The researchers will approach patients scheduled for primary ACLR and are eligible for participation in the study. Anesthesiology/Sports Medicine attendings, fellows, residents, and authorized researchers will consent and enroll patients pre-operatively.

3.1 Inclusion Criteria

- Patients between 18 and 75 years of age
- Patients undergoing primary ACL reconstruction with BPTB Autograft
- ASA I or II

3.2 Exclusion Criteria

- Patients younger than 18 and older than 75.
- Patients with multi-ligament injury
- Patients undergoing concomitant cartilage procedure or osteotomy.
- Patients with a history of chronic pain that have used opioids for pain management for 3 months or longer.
- Patients who are allergic to oxycodone;
- Patients with diagnosed or self-reported cognitive dysfunction;
- Patients with a history of neurologic disorder that can interfere with pain sensation;
- Patients with a history of drug or recorded alcohol abuse;
- Patients who are unable to understand or follow instructions;
- Patients with severe liver disease, renal insufficiency, congestive heart failure, and/or significant heart disease;
- Patients with an allergy or contraindication to any of the medications used in the study, or patients with a contraindication to any study procedures;
- Patients with a BMI over 45;
- Any patient that the investigators feel cannot comply with all study related procedures;
- Any pregnant patient; assessed via urine pregnancy test in the preoperative area as part of standard preoperative surgical protocol;

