Endpoint	Primary Endpoint: Opioid utilization for the first 72 hours after surgery, including during surgery, calculated as morphine equivalent. Secondary Endpoints: Opioid consumption Post-operatively Patient reported VAS scores in PACU Length of stay in PACU Patient reported VAS scores on POD 1, POD 2, POD 3, POD 7 Reaction to IPACK block Incidence of postoperative complications
Study Duration	The study will continue until 50 subjects are enrolled per arm, to allow for potential dropout and increased power.
Participant Duration	Each participant will be enrolled on DOS and complete their final follow up on postoperative day seven.
Duration of IP administration	Once during surgery
Population	50 patients per study arm scheduled for ACLR with BPTB autograft
Study Sites	NYU Langone Orthopedic Hospital and NYU Ambulatory Surgery Center at 38 th street
Number of participants	100
Description of Study Agent/Procedure	Patients in both the study and control group will receive the standard of care adductor canal block composed of 15 mL of Bupivacaine (0.25%). Patients in the study group will receive the additional IPACK block performed using 20 mL of Bupivacaine (0.25%) injected into the interspace between the popliteal artery and capsule of the knee. Patients will be blinded to their group allocation.
Reference Therapy	Reference is isolated adductor canal block
Key Procedures	Adductor canal block 15 mL 0.25% Bupivacaine, IPACK block with 20 mL 0.25% bupivacaine

CONFIDENTIAL

This material is the property of the NYU School of Medicine and Langone Medical Center. Do not disclose or use except as authorized in writing by the study sponsor

Statistical Analysis	Continuous and categorical baseline characteristics will be compared using Hedges standardized difference. Normally distributed data will be compared using t tests while non-normally distributed continuous outcomes will be assessed using the Mann-Whitney U test.
----------------------	--

CONFIDENTIAL

This material is the property of the NYU School of Medicine and Langone Medical Center. Do not disclose or use except as authorized in writing by the study sponsor

1 Background and Specific Aims

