4.2 Study Schedule

4.2.1 Screening

Screening Visit (Pre-surgical office visit -30 to -1 days)

- Review medical history to determine eligibility based on inclusion/exclusion criteria.
- Review medications history to determine eligibility based on inclusion/exclusion criteria.
- Provide participants with further details regarding their participation on day of surgery and follow up.

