6.2 Analysis of Endpoints

Primary Endpoints:

1. Opioid utilization for the first 24 hours after surgery, including during surgery, calculated as oral morphine equivalent.

CONFIDENTIAL

This material is the property of the NYU School of Medicine and Langone Medical Center. Do not disclose or use except as authorized in writing by the study sponsor

Secondary Endpoints:

1. Patient reported VAS scores in PACU
2. Length of stay in PACU
3. Patient reported VAS scores on POD 1, POD 2, POD 3, POD7
4. Reaction to IPACK block
5. Mid-term functional outcomes will be assessed at 6 months: VAS, KOOS-PS, KUJALA, Tegner Activity Scale, strength, ROM.

Normally distributed data such as the primary outcome variable will be compared using the two-sample t-test. In the case that the data are not normally distributed, the Wilcoxon rank-sum test will be used instead. Categorical variable will be compared using the Chi-Squares unless other tests such as the Fisher's exact test are more appropriate.

All endpoints will be evaluated as fits the data set with graphical figures such as scatter plots, box-and-whisker plots, and frequency histograms to visualize the distribution of these outcomes and their relationships to covariates and treatment assignment. When appropriate descriptive graphical and tabular methods will also be estimated and presented in a graphical figure.

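### Section 3.2 lets patients on current prescribed opioids enrol, and the unadjusted primary test on total opioid consumption does not account for that use

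*Combined protocol and SAP*

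**What the plan says.** **Eligibility.** Section 3.2 excludes "Patients with a history of chronic pain that have used opioids for pain management for 3 months or longer". The nearest neighbouring item excludes "Patients with a history of drug or recorded alcohol abuse", which does not reach a short prescribed course. The oxycodone-allergy, contraindication and compliance items do not reach it either. Section 3.1 sets age, ASA class and procedure ("Patients undergoing primary ACL reconstruction with BPTB Autograft") and does not require opioid-naive patients.

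**Checks before surgery.** Section 4.2.1 asks staff to "Review medications history to determine eligibility based on inclusion/exclusion criteria". Section 4.2.2 verifies the same criteria on day 0. Neither adds an opioid limit.

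**Endpoint.** Section 6.2 gives the primary endpoint as "Opioid utilization for the first 24 hours after surgery, including during surgery, calculated as oral morphine equivalent". The Protocol Summary gives it as "Opioid utilization for the first 72 hours after surgery, including during surgery, calculated as morphine equivalent". Home use enters through follow-up contacts that "collect additional data on opioid use at home as well as a VAS score at 24, 48, and 72 hours after surgery" (section 2.1). Nothing subtracts pre-operative use.

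**Analysis.** Section 6.2 says: "Normally distributed data such as the primary outcome variable will be compared using the two-sample t-test". A rank-sum test replaces it if the data are not normal. Randomisation is in blocks of four with no stratification by opioid use (section 2.1). Section 6.2.1 lists medications among the recorded baseline data, but no analysis uses them.

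**The concern.** The outcome is the amount of opioid taken, so opioid use already under way before surgery is the baseline variable closest to it. The plan treats opioid exposure as relevant to eligibility, but its criterion addresses only long use combined with chronic pain. It passes someone who has taken a prescribed opioid daily for ten weeks and is still doing so. Read literally, it also passes someone with 3 months or more of use but no chronic-pain history.

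Doses taken before surgery fall outside the endpoint. Use that continues afterwards, and any raised requirement that follows from earlier use, falls inside it. In an unadjusted comparison this widens the spread of the endpoint. With 50 per arm, an uneven split of such patients also moves the estimated difference. The likely cost is power, in a trial whose allowance above the calculated sample size is only 8 patients per arm.

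**Working it through.** **The plan's own figure.** Section 6.3 states a two-sided two-sample t-test, α = 0.05, power 0.80 and 42 per group for a moderate effect, which it does not quantify. Solving the exact (noncentral t) power equation for n = 42 gives d = 0.619. By the normal approximation, d = (1.960 + 0.842) × √(2/42) = 0.611. If moderate meant d = 0.5, the exact calculation would need 64 per group, so 42 can be neither confirmed nor refuted. I take d = 0.619 as the effect the plan is sized for. At 50 per arm its power is 0.865.

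**Assumptions (not in the documents).** A share q of patients are pre-operative users, and their total is higher by E opioid-naive SDs in both arms. I take q = 3%, 5% and 10%, with E = 2 and 4.

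**Formulas.** Endpoint SD becomes √(1 + q(1−q)E²) in opioid-naive SDs, and the effective effect size is 0.619 divided by that. Example for q = 5%, E = 2: √(1 + 0.05 × 0.95 × 4) = √1.19 = 1.091, so d = 0.619/1.091 = 0.567.

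The t-test column below is exact. The rank-sum column is from simulation of the same mixtures, so its second decimal is approximate.

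| Users q | Excess E | SD factor | Power, t-test | Power, rank-sum |
|---|---|---|---|---|
| none | – | 1.00 | 0.865 | – |
| 3% | 2 SD | 1.06 | 0.826 | about 0.82 |
| 5% | 2 SD | 1.09 | 0.802 | about 0.80 |
| 10% | 2 SD | 1.17 | 0.747 | about 0.74 |
| 3% | 4 SD | 1.21 | 0.716 | about 0.79 |
| 5% | 4 SD | 1.33 | 0.636 | about 0.76 |
| 10% | 4 SD | 1.56 | 0.500 | about 0.68 |

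The two tests agree at 2 SD. At 4 SD the data are plainly not normal, so the rank-sum column is the one the plan would use. With a 1 SD excess the loss is small: at q = 10% the t-test power is 0.835.

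**Chance imbalance.** The SD of the shift in the arm difference is E × √(2q(1−q)/50). For q = 10%, E = 2 this is 2 × √(0.18/50) = 0.12 opioid-naive SDs, against a target difference of 0.62.

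**Scale in milligrams.** Attachment 15.1 converts oral oxycodone at 1.5. An assumed 20 mg a day gives 20 × 1.5 = 30 mg OME over 24 hours, or 90 mg over 72 hours. Over 24 hours, 30 mg equals 2 SD if the opioid-naive SD is 15 mg, and 4 SD only if it is 7.5 mg, the OME of a single 5 mg tablet. The endpoint also counts intraoperative opioid, and 0.1 mg of intravenous fentanyl alone is 15 mg OME in the same table. This makes 4 SD an extreme case for that example.

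**With adjustment.** In simulations of the same mixtures, a linear model with arm and a yes/no indicator of pre-operative use held power at about 0.86 in every scenario. That is a best case, because the simulated excess is a constant that the indicator captures fully.

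**The case against.** A duration-based exclusion of chronic users is a legitimate pragmatic choice, and randomisation protects the comparison. Both points stand. A reader might infer that admitting current users biases the treatment effect, but the documents do not support that: allocation is random, so only noise and chance imbalance follow.

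The low t-test powers (0.72–0.50 at 4 SD) do not represent the plan, because section 6.2 switches to a rank-sum test when normality fails. That also stands, and it removes the worst figures. It gives no protection at 2 SD.

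A reader might go further and say that carried-over use cannot respond to the block. The documents do not show this. If the opioid was prescribed for the injured knee, later use may be driven by pain that the block could affect. Section 2.1 also names an oxycodone product for post-operative pain, so the study regimen may replace earlier use rather than add to it.

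A reader might also object that remote long-term use is excluded. That happens only with a chronic-pain history, and nothing in the documents shows that it harms the trial.

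Finally, neither the share of users nor the endpoint SD is given. This limits what can be said about size, but it does not close the gap in the text.

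**Conclusion.** The gap holds on the text, under either the 24-hour or the 72-hour window (that conflict is a separate matter). Current prescribed opioid users can be enrolled, and neither the randomisation nor the primary analysis takes account of it. The consequence is lost precision and chance imbalance, not systematic bias.

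The size rests on assumed shares of 3–10% and an assumed excess of 2–4 SD, at d = 0.62 and 50 per arm with no dropout. From about 0.86, power falls to about 0.82–0.74 at 2 SD under either test, and to about 0.79–0.68 at 4 SD under the rank-sum fallback. At 5% and 2 SD, the margin gained by enrolling 50 rather than 42 is essentially used up. If users are rarer or their excess is smaller, the loss is minor. The change is worth making because it is cheap and the variable is easy to collect.

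**What to change.** 1. At the section 4.2.1 medication review, and again at the section 4.2.2 day-0 verification, record any opioid use in a prespecified period before surgery. Thirty days is an example; the window is an assumption that the sponsor should justify.
2. In section 6.2, replace the unadjusted primary comparison with a linear model of opioid consumption on arm plus pre-operative opioid use (yes/no). State in advance that a transformation or robust standard errors will be used if the data are skewed.
3. Keep the rank-sum test as a sensitivity analysis, and report pre-operative opioid use by arm at baseline.

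The cost is one extra question and a real change of primary method, since a covariate cannot be added to a two-sample t-test or rank-sum test. No patients are lost.

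A recency limit in section 3.2 is an optional alternative for the sponsor. It would remove the source of the variance, but it narrows the population and loses some otherwise eligible patients.
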